7.2 PARTICIPANT DISCONTINUATION/WITHDRAWAL FROM THE STUDY

Participants are free to withdraw from participation in the study at any time upon request. An investigator may discontinue a participant from the study for the following reasons:

- 1. Participant has not completed an acupuncture treatment for > 14 days, unless a participant has an illness, such as COVID-19. In this case, additional time may be allowed, as determined by the investigator.
- 2. Significant study intervention non-compliance
- 3. Lost-to-follow up; unable to contact subject (see Section 7.3, Lost to Follow-Up)
- 4. Any event or medical condition or situation occurs such that continued collection of follow-up study data would not be in the best interest of the participant or might require an additional treatment that would confound the interpretation of the study
- 5. The participant meets an exclusion criterion (either newly developed or not previously recognized) that precludes further study participation

The reason for participant discontinuation or withdrawal from the study will be recorded on the relevant eCRF. Subjects who sign the informed consent form and are randomized but do not receive the study intervention may be replaced. Subjects who sign the informed consent form, and are randomized and receive the study intervention, and subsequently withdraw, or are discontinued from the study, will not be replaced.

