5.2 EXCLUSION CRITERIA

An individual who meets any of the following criteria will be excluded from participation in this study:

- Non-English speaking
- Participation in acupuncture treatment outside of the study, while enrolled
- History of pre-existing primary headache, defined as more than 12 days of tension-type headache annually and/or more than one migraine attacks per month in the last year⁴
- History of any other serious neurological, psychiatric, chronic pain disorders, or seizures
- History of bleeding diathesis, other bleeding disorders, or syncope with needle puncture
- History of cardiac arrhythmia or current pacemaker, neurostimulator, or other implanted stimulation device
- Recent or active substance use disorder
- Women who are currently pregnant, lactating, or planning to become pregnant during the study
- Any other medical conditions that could affect their ability to participate in acupuncture treatments for the study duration (as determined by study investigators)
- Active participation or past participation ≤3 months in any other interventional study.
- Unwilling to participate in all study related activites

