6.3 MEASURES TO MINIMIZE BIAS: RANDOMIZATION AND BLINDING

Randomization:

Randomization will be performed with a 1:1 allocation ratio. Balanced treatment assignments will be achieved using permuted block randomization with random block sizes stratified by gender. This decision was based on evidence that females in this population reported higher rates of headaches.³³ The study biostatistician will generate a randomization schedule using the SURVERYSELECT procedure in SAS. Assignments will not be seen by other study personnel in advance and will not be changed after randomization.

Blinding:

Study personnel will be unblinded to the randomization, as it will be clear the number of participants who receive 5 acupuncture treatments versus those that receive 10. In addition, it will be clear to participants which treatment group they are in and it will be impossible to blind them from this information.

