6.5 CONCOMITANT THERAPY

For this protocol, participants may use non-opioid analgesics for pain control, including over-the-counter medications and dietary supplements, and prescribed medications. This includes use for rescue therapy in the event of exacerbation of symptoms due to acupuncture treatment. Medication usage will be assessed at each study visit and documented in the relevant eCRF.

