9.4.2 ANALYSIS OF THE PRIMARY ENDPOINT(S)

The number of headache days per 4 weeks will be captured via a headache diary. The primary outcome, change in number of headache days per 4 weeks between the pre-treatment assessment and 4-week post treatment assessment, will be compared using a two sample t-test. We will present the mean change by group with corresponding standard deviations. If baseline differences are found between study groups, they will be adjusted for using a linear regression model. In addition, a mixed-model analysis of variance (ANOVA) will be performed with data from all three time points. The outcome will be number of headache days per 4 weeks and it will be adjusted for group, time, and a group*time interaction. If significant interactions exist, line plots and post hoc tests will be used to define the nature of the interaction.

Prior to analysis, we will plot our outcomes to examine their distribution and decide whether we should consider non-parametric analyses. Only subjects with complete data from both pre-treatment assessment and 4-week post treatment assessment will be included in the final analysis. Data will be analyzed per an intent-to-treat approach regardless of actual treatment received. If a large proportion of missing data is noted, we will compare baseline characteristics of subjects who completed the treatment with those who were lost to follow-up.

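### Section 7.2 items 4 and 5 let investigators who know the arm end a participant's follow-up before the primary diary is complete, so missing outcomes can depend on response and arm despite the stated intention-to-treat analysis

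*Combined protocol and SAP*

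**What the plan says.** Section 7.2 opens its list with "An investigator may discontinue a participant from the study for the following reasons". The grounds apply to the study as a whole, not only to the acupuncture sessions.

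- Item 4 has two limbs. One is that further follow-up data collection would not serve the participant's best interest. The other is that an event, condition or situation "might require an additional treatment that would confound the interpretation of the study". What counts as confounding is not defined.
- Item 5 reads: "The participant meets an exclusion criterion (either newly developed or not previously recognized) that precludes further study participation". Section 5.2 lists one criterion that can only arise after entry, "Participation in acupuncture treatment outside of the study, while enrolled", and one for other medical conditions that is left to judgement, "as determined by study investigators".

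Section 6.3 states: "Study personnel will be unblinded to the randomization". No masked review of withdrawals is described.

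Section 7.1 treats an investigator-decided discontinuation as withdrawal from the study. It then plans one call at 7 to 14 days for AEs and SAEs, with no headache diary.

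Section 9.4.2 limits the final analysis to participants with complete data at baseline and 4 weeks post-treatment, yet the next sentence says "Data will be analyzed per an intent-to-treat approach regardless of actual treatment received". Section 9.3 makes the same intention-to-treat statement for all analyses.

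Other text bears on how far items 4 and 5 reach. Section 6.5 permits non-opioid analgesics, "including over-the-counter medications and dietary supplements, and prescribed medications". Section 9.4.9 expects medication regimens to change and excludes those participants only in a sensitivity analysis. Section 8.3.9 lets a participant who becomes pregnant after her last session stay to the end of the study.

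**The concern.** Two of the grounds for ending follow-up can be related to how the participant is doing. In a headache trial, needing a further treatment or seeking acupuncture elsewhere may follow a poor response. The person deciding knows whether the participant was assigned 5 or 10 sessions. Neither item requires that study acupuncture was stopped or missed.

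A participant removed before the post-treatment diary is complete leaves the primary analysis, and no planned step recovers the information. The plan has no imputation and no sensitivity analysis for data missing not at random. Its only check is a comparison of baseline characteristics if much data is missing. Section 9.2 treats attrition purely as lost power. At stake is a bias of unknown sign in the 10-versus-5 contrast, and a type I error above 5%. With 18 per arm, a few removals are enough to matter.

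**Working it through.** **The plan's own figure.** Inputs from 9.2: 18 per arm, two-sided t-test, alpha 0.05, difference 4.5 days (26 versus 21.5), SD 4.47 (shown as 4.5 in the tables). The noncentrality is 4.5 / (4.47 × √(2/18)) = 4.5 / 1.49 = 3.02 on 34 degrees of freedom. Power is 0.835, as stated. N = 30 gives 0.758, also as stated. With SD 4.5, used below, N = 36 gives 0.830. These rows allow for a smaller sample only. They assume that the people lost are like those who stay.

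**Illustration of outcome-related removal.** The documents give no removal rate, so the counts and correlations are assumptions. Outcomes are normal with means 26 and 21.5 (equal means for the null), SD 4.5, 18 per arm. In each arm, the participants with the highest score on a removal propensity are dropped. That propensity has correlation ρ with final headache days. A two-sided t-test is run on those left.

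Under normality the shift in the difference is ρ times its value at perfect ranking. For 3 versus 1 removed, perfect ranking gives 3.71, a shift of 4.5 − 3.71 = 0.79. Then:

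- ρ = 0.5: 4.5 − 0.5 × 0.79 = 4.1 days
- ρ = 0.3: 4.5 − 0.3 × 0.79 = 4.3 days

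Simulated results:

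| Removed (5 v 10 sessions) | ρ | Difference (days) | Power | Rejection under the null |
|---|---|---|---|---|
| 0 v 0 | – | 4.5 | 0.83 | 0.05 |
| 3 v 1 | 0 | 4.5 | 0.78 | 0.05 |
| 3 v 1 | 0.3 | 4.3 | 0.74 | 0.05 |
| 3 v 1 | 0.5 | 4.1 | 0.73 | 0.06 |
| 3 v 1 | 1 | 3.7 | 0.72 | 0.11 |
| 3 v 0 | 0.3 | 4.1 | 0.73 | 0.06 |
| 3 v 0 | 0.5 | 3.9 | 0.68 | 0.07 |
| 3 v 0 | 1 | 3.2 | 0.58 | 0.15 |

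The reverse pattern (1 v 3) inflates the difference by the same amounts: 4.5 + 0.3 × 0.79 = 4.7, 4.5 + 0.5 × 0.79 = 4.9, and 5.3 at ρ = 1.

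A different selection model gives similar results. If 2, 3 or 4 participants are removed at random from the worst third of one arm, with none from the other, null rejection is about 0.06, 0.09 or 0.14.

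**Ceiling.** The outcome cannot exceed 28 days, but a normal with mean 26 and SD 4.5 puts 1 − Φ(2/4.5) = 0.33 of the 5-session arm above 28. With a bounded (beta-binomial) outcome of the same means and SD, perfect 3 v 1 removal leaves the difference near 4.5. Null rejection for 3 v 1 or 3 v 0 is then between about 0.05 (mean 26) and 0.12 (mean 21.5).

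**Limit of the model.** It uses end-of-period levels, whereas 9.4.2 tests change from baseline.

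**The case against.** The strongest reply is that the large figures need an investigator who can rank participants on an outcome that has not yet been recorded. A removal that costs primary data must come before the post-treatment diary is complete. The visit descriptions in 1.3 start the three diary periods at the pre-treatment visit, the last acupuncture visit and the 4-week visit, so no diary runs during the treatment weeks. This stands. The values of 0.11 to 0.15 are an extreme, and the rows for ρ of 0.3 to 0.5 are the more useful guide.

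The text also narrows the triggers, and several stronger readings that a reader might infer are not supported:

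- *Item 4 flatly contradicts 6.5, or mostly means headache that did not improve.* It covers any event or condition whose treatment would confound. Read with 6.5 and 9.4.9, ordinary analgesic or prescription changes need not trigger it. The fault is that the boundary is undefined.
- *Low-dose participants are the likeliest to seek acupuncture elsewhere.* This is plausible, but nothing in the documents shows it.
- *Item 5 catches anyone who newly meets an exclusion criterion.* It is limited to criteria that preclude further participation, and 8.3.9 keeps one such group in follow-up.
- *Every removed participant is lost to the primary analysis.* Someone removed after the 4-week diary has the data that 9.4.2 requires, and nothing says those data are discarded. What is lost is the 12-week data used in the mixed model.

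The power is also discretionary, and reasons are recorded on the eCRF. Recording a reason does not recover the outcome, and discretion exercised with knowledge of the arm is the source of the risk. The harm comes from 7.2 together with 7.1 and 9.4.2, not from 7.2 alone.

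**Conclusion.** The concern holds as a statement of what the plan permits. Investigators who know the arm may end follow-up on grounds that can depend on response. The diary then stops, and the complete-case rule drops anyone removed before the 4-week data are in. That is inconsistent with the intention-to-treat statements in 9.3 and 9.4.2.

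The likely size is modest. Under assumed removals of 3 versus 1 or 3 versus 0 of 18, and a weak to moderate relation to outcome, the type I error is about 0.05 to 0.07. For 3 versus 1 the 4.5-day difference becomes about 4.1 to 4.3 days, or about 4.7 to 4.9 if the pattern is reversed. The upper extreme is 0.11 to 0.15, with 3.7 days for 3 versus 1.

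A reader might infer that such bias has occurred, because 10.4 records enrolment raised to 40 on account of withdrawals. That entry gives neither arm nor reason. It shows that withdrawals happen, not that they are selective. The point should be fixed because the remedy is cheap and diary data not collected cannot be recovered in the analysis. It does not by itself invalidate the design.

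**What to change.** Confine the change to data collection and analysis. Decisions on when study acupuncture stops stay as they are.

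- In 7.1 and 7.2, state that discontinuation under items 4 and 5 does not by itself end data collection. Remove the confounding-treatment limb of item 4 as a ground for ending follow-up.
- Continue the diaries and the 4- and 12-week calls unless the participant withdraws consent or continued data collection is not in the participant's best interest. The second exception is the other limb of item 4 and is kept.
- At those two existing calls, record outside acupuncture and new headache treatment (yes/no, date).
- In 9.3 and 9.4.2, state that these participants are analysed in their randomised arm, and report withdrawals by arm and reason.
- Reconcile 7.2 with 6.5, 8.3.9, 9.3 and 9.4.2, so that the same additional treatment is not accepted in one section and a possible ground for removal in another.

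The cost is protocol wording, a short question at two calls already scheduled, and slightly more follow-up work. The estimate will then include the effect of additional treatments, which is what an intention-to-treat comparison of the two schedules implies.

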7.3 LOST TO FOLLOW-UP

A participant will be considered lost to follow-up if he or she fails to attend any scheduled study visit and study staff are unable to contact the participant after at least 5 attempts, while maintaining the 14 day maximum between visits.

The following actions must be taken if a participant fails to attend any required study visit:

• Study staff will attempt to contact the participant, reschedule the missed visit, counsel the participant on the importance of maintaining the assigned visit schedule and ascertain if the participant wishes to and/or should continue in the study.

- Before a participant is deemed lost to follow-up, the investigator or designee will make every
 effort to regain contact with the participant (where possible, telephone calls or e-mail if no
 answer leave a voicemail on the first and last attempt). These contact attempts will be
 documented.
- Should the participant continue to be unreachable, he or she will be considered to have withdrawn from the study with a primary reason of lost to follow-up.

8 STUDY ASSESSMENTS AND PROCEDURES

8.1 ENDPOINT AND OTHER NON-SAFETY ASSESSMENTS

Demographics: Demographic information will be collected, including: gender, age, race, ethnicity, language, height, weight, marital status, employment status, date of TBI, date of CPTH diagnosis, and email address for Headache Diary surveys (discussed below).

Medication Review: Medication data will be used for exploratory purposes for Specific Aim 3.

Headache Diary: Participants will be sent an e-mail REDCap survey to complete and asked to record headache information for three 4-week time periods. During each 4-week period, they will receive the e-mail once per week. They will be provided paper headache diaries (Appendix 1-3) to keep track of their headaches and will be asked to complete each e-mail survey they receive. The headache diary survey will include: how many headaches occurred each week during the 4-week period, duration, pain intensity (0-10 scale), type (e.g. tension), and name of medication taken and dosage (if applicable). The outcome measure for Specific Aim 1 is number of headache days over 4 weeks; other variables will be exploratory.

Treatment Adherence: The participant's treatment adherence will be measured to determine tolerability of acupuncture. We will record the number of attended acupuncture sessions. We will also record participants' ability to maintain the acupuncture duration of 30 minutes per session.

Sleep: Participants will be asked to complete the Pittsburgh Sleep Quality Index (PSQI), which contains questions about one's usual sleep habits during the past month.

Quality of Life: Participants will be asked to complete the TBI-QOL short forms. The TBI-QOL includes the following domains: ability to participate in social roles and activities, anger, anxiety, attention-concentration, cognition-general concerns, communication, depression, emotional behavior dyscontrol, executive function, fatigue, grief-loss, headache pain, independence, learning-memory, mobility, pain interference, positive affect and well-being, resilience, satisfaction with social roles and activities, self-esteem, stigma, and upper extremity.

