 - © E-mail the Pittsburgh Sleep Quality Index (PSQI) and Traumatic Brain Injury-Quality of Life (TBI-QOL) surveys to the patient for completion. Ask patients to complete the surveys prior to their first acupuncture visit. During the reminder call for the acupuncture visit, patients will be reminded to complete the surveys if they have not yet completed them.
 - Provide participants instructions regarding the Headache Diary REDCap survey (example script below):
 - "You will receive a Headache Diary survey via e-mail once a week for the next 4 weeks. Each survey will ask questions about your headaches over the last week. What is most important for you to remember is the number of headaches you had. The rest of the information is also helpful."
 - 2. Provide participants a paper diary and ask them to use it to keep track of their headaches during the week. Instruct participants that they should use it to fill out the weekly e-mail survey.
 - 3. Show participants an example of the REDCap survey.

3. Study Intervention

- Duration: Each visit approximately 1 hour
- A study acupuncturist will:
 - Complete the Adverse Events (AE) Reporting, Medication Review, and Treatment Adherence in the relevant eCRFs in REDCap.
 - o Perform the acupuncture treatment.
- Only at the LAST acupuncture visit, a study acupuncturist will:
 - Provide participants instructions regarding the Headache Diary REDCap survey (example script below):
 - "Like you experienced before, you will receive a Headache Diary survey via e-mail once a week for the next 4 weeks. Each survey will ask questions about your headaches over the last week. What is most important for you to remember is the number of headaches you had. The rest of the information is also helpful."

2. Provide participants a paper diary and ask them to use it to keep track of their headaches during the week. Instruct participants that they should use it to fill out the weekly e-mail survey.

3. Show participants an example of the REDCap survey.

4. 4-week Post-treatment Visit

- Duration: Approximately 30 minutes via phone
- Research staff will:
 - Complete the AE Reporting and Medication Review forms in the relevant eCRFs in REDCap.
 - o E-mail the PSQI and TBI-QOL surveys to the patient for completion. Ask patients to complete the surveys within one week. Five days after the visit, patients will receive a reminder call if they have not yet completed the surveys.

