2 INTRODUCTION

2.1 BACKGROUND & STUDY RATIONALE

Chronic post-traumatic headache (CPTH) after a mild traumatic brain injury (mTBI) is extremely debilitating, dramatically impacts function and quality of life, and is the most frequent type of chronic pain reported after injury.¹ It has been estimated that approximately 17.1 million Americans suffer a traumatic brain injury (TBI) each year,² with CPTH estimated to occur in 57.8% of these individuals.³ CPTH presents as: 1) tension-like (mild-moderate dull pain), 2) migraine headache (moderate-severe throbbing pain), or 3) combined tension-like and migraine headache.¹ On average, the number of reported headache days each month for individuals suffering from CPTH is 26,⁴ which is almost daily. Individuals suffering from CPTH are more likely to have post-traumatic stress disorder, cognitive symptoms, and somatic symptoms.⁴ They are also more likely to perceive difficulties in their physical and social function.⁴ Consequently, it is not surprising that CPTH is extremely agonizing and frustrating for individuals with mTBI.

There are currently no FDA approved pharmacological treatments specifically for CPTH and the long-term effects of pharmacologic treatments on recovery after TBI are unclear. Thus, individuals are typically prescribed medications that target the particular type of headache (e.g. triptan for a migraine headache). Non-narcotic analgesics, nonsteroidal anti-inflammatory drugs (NSAIDs), and triptans are often prescribed for headache and migraine treatment and have been recommended to be coupled with non-pharmacological treatments, such as physical therapy, biofeedback, and relaxation training. However, because the long-term effects of pharmacologic treatments on recovery after TBI are unclear, non-pharmacologic or behavioral treatments for CPTH are very appealing.

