3 OBJECTIVES AND ENDPOINTS

OBJECTIVES	ENDPOINTS
Primary	
To determine the effect of a low versus high dose of acupuncture on number of headache days per month in individuals with mTBI suffering from CPTH.	Number of headache days over 4 weeks
Secondary	
To determine the safety and tolerability of acupuncture on CPTH in individuals with mTBI.	Adverse or Serious Adverse Events Completion of treatment durations and sessions
Exploratory	
To explore the effects of acupuncture on sleep, quality of life, headache outcomes, and	 Pittsburgh Sleep Quality Index Traumatic Brain Injury-Quality of Life

OBJECTIVES	ENDPOINTS
medications in individuals with mTBI who suffer	3. Headache Outcomes
from CPTH.	4. Medications

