9.2 SAMPLE SIZE DETERMINATION

We require 18 subjects in each study group to achieve 80% power at a 5% significance level for our primary hypothesis (PASS software version 11). The primary analysis is a a two-sided two-sample t-test comparing the mean number of headache days over 4 weeks from a parallel-group design. We hypothesize that, while both groups will have decreased headaches, 10 treatments will greater alleviate headaches when compared to 5 treatments over a 5-week treatment period. For analysis purposes, we will analyze the data such that the opposite could be shown (5 treatments better reduces headaches). The null hypothesis is that there will be no difference between treatment groups. To conduct the power calculation, we assumed an equal standard deviation of 4.47, 33 equivalence limits of ± 1 SD, and a true difference between means of 0. No interim analyses are planned. The potential effect on our power if our estimates for the effect size are inaccurate are displayed in the table below.

N	δ	Σ	Power	Alpha
36	4	4.5	0.742	0.05
36	4.5	4.5	0.835	0.05
36	5	4.5	0.903	0.05

N = total sample size; δ = treatment effect (change); σ = standard deviation.

Based on preliminary estimates, we do not anticipate difficulty recruiting 40 subjects. HealthPartners Physical Medicine and Rehabilitation physicians see approximately 25 individuals with CPTH per month at the Neuroscience Center. Therefore we will need a 16% enrollment rate to reach our recruitment goal in the allotted time frame. In addition, we also plan to recruit and enroll from other HealthPartners clinics and within the community. If we see a 20% reduction in sample size due to dropout, withdrawal, or missing data, our power will be 75.8% to detect a similar effect size. This, and other possible changes in power due to attrition, are listed in the table below.

N	μ1	μ2	δ	σ	Power	Alpha
28	26	21.5	4.5	4.5	0.727	0.05

30	26	21.5	4.5	4.5	0.758	0.05
32	26	21.5	4.5	4.5	0.787	0.05
36	26	21.5	4.5	4.5	0.835	0.05

N = total sample size; μ 1 = mean of 5 treatment group; μ 2 = mean of 10 treatment group; δ = treatment effect (change); σ = standard deviation.

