9.4.9 EXPLORATORY ANALYSES

Exploratory outcomes (headache: intensity, duration, type; sleep; and QOL) will be compared between groups with Student's t-test, Chi-square test, and Mann-Whitney-U test and mixed-model ANOVAs, as appropriate. As an exploratory analysis, patients who report post-COVID-19 symptoms will be identified using the additional COVID-19 set of questions. Types and severity of post-COVID-19 symptoms present within the group will be described. The t-test or non-parametric equivalent will be used to determine whether acupuncture had an effect on post-COVID symptoms.

As some patients' medication adherence and regimens are expected to change throughout the intervention period, a sensitivity analysis will be performed for all primary and secondary endpoints in which we exclude patients with medication regimen ammendments. These results will be compared to our main analysis to help contextualize any observed intervention effect. Patients with and without changes to their medications during the trial will be described separately and any differences will be presented. If necessary, we will conduct a sensitivity analysis in which we exclude participants that had protocol deviations (e.g. large delays between treatments) due to illness, for example COVID-19.

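### The primary endpoint is headache days, but the diary survey and the participant scripts are worded in numbers of headaches, and neither a days item nor a headache day is defined.

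*Combined protocol and SAP*

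**What the plan says.** Section 3 gives the primary endpoint as "Number of headache days over 4 weeks". Section 9.2 bases the sample size on a two-sided t-test "comparing the mean number of headache days over 4 weeks from a parallel-group design". Section 9.4.2 tests the change in this number from the pre-treatment to the 4-week post-treatment assessment and says that the headache diary supplies it.

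Section 8.1 describes the diary. Participants keep a paper diary (Appendix 1-3) and from it answer a weekly e-mail survey during three 4-week periods. The survey is to include "how many headaches occurred each week during the 4-week period", together with duration, pain intensity, type, and medication with dosage. The paragraph ends: "The outcome measure for Specific Aim 1 is number of headache days over 4 weeks; other variables will be exploratory".

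Section 1.3 gives an example script for starting each diary period: at the pre-treatment visit, at the last acupuncture visit and at the 4-week post-treatment visit. All three say: "What is most important for you to remember is the number of headaches you had". At each of these points staff hand over the paper diary and "ask them to use it to keep track of their headaches during the week".

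**The concern.** The quantity that participants are asked to report, as described, is not the quantity that is analysed. Several headaches can fall on one day, and one headache can span several days, so a weekly number of headaches does not fix the number of days with headache. The listed duration item does not close the gap, because no dates and no derivation rule are described.

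The first two scripts open the two diary periods that give the primary change score. The third opens the period that adds the last time point of the mixed model. The same wording therefore reaches every value of the primary outcome. If participants report episodes where the analysis expects days, the comparison of 5 with 10 treatments is made on a different scale from the one in the protocol. Different participants may also read the question differently.

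**Working it through.** **1. The planned analysis is on days.** Section 9.2 gives N = 36 (18 per group), a difference of 4.5 (means 26 and 21.5), SD 4.5 and two-sided alpha 0.05. The noncentrality parameter is δ / (σ√(2/n)) = 4.5 / (4.5 × √(2/18)) = 3.00 with 34 degrees of freedom. This gives power 0.830, against 0.835 in the plan. The other five rows of the two power tables also reproduce to within 0.01. The mean of 26 matches the background in section 2.1: "On average, the number of reported headache days each month for individuals suffering from CPTH is 26". The SD of 4.47 is stated without a unit; that it is in days is inferred from its use beside these means.

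**2. The described measurement, set beside the endpoint.**

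| Place | Quantity named |
|---|---|
| Sections 3, 9.2, 9.4.2 and the last sentence of the diary paragraph in 8.1 | Headache days |
| Section 8.1, survey content | Headaches per week |
| Section 1.3, three example scripts | Number of headaches |
| Any section: rule from count to days | None given |
| Any section: definition of a headache day | None given |

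**3. The two quantities can differ and can move in opposite directions.** These are illustrations, not trial data.

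- A week with headache on all 7 days gives a count of 1 for one continuous headache, 7 for one a day, and 7 × 2 = 14 for two a day.
- Suppose that a week with one continuous 7-day headache (count 1, days 7) is later followed by a week with four separate one-day headaches (count 4, days 4). Days fall by 3 while the count rises by 3.

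**4. Scale per weekly survey.** The planning means are 26/4 = 6.5 and 21.5/4 = 5.375 headache days per survey, so the planned difference is 4.5/4 = 1.125 days per survey. Days cannot exceed 7 in a survey or 4 × 7 = 28 in a period. A count of headaches has no such limit.

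**5. What cannot be computed.** The documents give no number of headaches per headache day and no mean or SD for headache counts. No corrected power or bias figure follows.

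**The case against.** The strongest reply is that this is loose wording. Section 9.1, under the headache-days endpoint, states its hypotheses as a reduction in headaches, and section 9.2 does the same in the paragraph that specifies a t-test on headache days. The sponsor plainly uses headaches as shorthand for this endpoint. Section 9.4.2 says that the diary yields days. The list in section 8.1 says what the survey will include and need not be complete. The scripts are labelled as examples, and participants are also shown a sample survey. The survey form and Appendix 1-3, which could settle the matter, were not among the documents reviewed.

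Most of this stands, and it limits the conclusion. It does not remove the point: even if the forms ask for days, the scripts tell participants that another quantity matters most, and the protocol text leaves a headache day undefined.

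A reader might infer that the headache count must be the source of the primary endpoint, because section 9.4.9 names other diary items as exploratory ("Exploratory outcomes (headache: intensity, duration, type; sleep; and QOL) will be compared between groups") and leaves the count out. The documents do not support that inference. The statement in section 8.1 that the other variables are exploratory can cover the count, and section 3 lists headache outcomes as exploratory without restriction.

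**Conclusion.** The mismatch in wording is certain, and it concerns the primary endpoint. As described, the survey collects a quantity that does not determine the one that is tested. It should be corrected.

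The size of any effect is unknown. The illustrations show that counts and days can diverge widely in one week; they do not estimate how often this happens in the trial.

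A reader might go further and conclude that the endpoint cannot be computed from the collected data. That would follow only if the fielded survey matches its description and the paper diaries do not fill the gap. Neither is shown. If the forms prove to have no days item, the point becomes much more serious, because section 9.4.2 restricts the primary analysis to participants with complete data at both assessments. If the forms do record days, what remains is misleading wording and a missing definition.

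**What to change.** In either case:

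- Change the survey description in section 8.1 and the three example scripts in section 1.3 to *the number of days on which you had a headache*.
- Define a headache day, for example any headache on that calendar day.
- Define the endpoint as the sum of the four weekly values.
- Check the fielded survey and the paper diary before analysis.

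If the survey has no days item:

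- Add one: *On how many of the last 7 days did you have a headache? (0-7)*.
- Keep the headache count as an exploratory outcome.
- Do not mix counts and days within one participant's change score.
- Report by arm how many participants have only a headache count.
- Recover days from the paper diaries only if these prove to be dated and to have been kept.

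If the forms already record days, the cost is a few wording edits. If they do not, it is one survey item and a minor amendment, with possible loss of the days endpoint for participants already enrolled. That loss could be considerable: the amendment history in section 10.4 shows enrolment under way by 2021, and the latest version dates from March 2023.
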